5.4 Dose Limiting Toxicity

Dose-limiting toxicities are defined as the following toxicities if they occur anytime within the first 5 weeks of starting azacitidine (anytime within Cycle 1) and are thought to be secondary to azacitidine in combination with daratumumab:

- Grade 4 neutropenia lasting more than 7 days.
- Grade 4 thrombocytopenia lasting more than 7 days despite transfusion support.

- Grade 3 or higher non-hematological toxicity except:
 - Grade 3 nausea, vomiting or diarrhea that can be controlled within 48 hours with maximal supportive care.
 - Grade 3 hyperglycemia that can be controlled within 48 hours with appropriate supportive care.
 - Asymptomatic new Grade 3 or higher electrolyte disturbances that can be controlled with repletion or other medical management within 24 hours.

Severity of AEs will be graded according to CTCAE Version 5.0. As described in [Section 8.2.2](#), interim analysis will occur after accrual of 6 patients in the safety cohort. Study accrual will be stopped until these 6 patients have completed at minimum 5 weeks of treatment after starting azacitidine (ie completed Cycle 1), at which point a formal interim safety analysis will be performed with assessment for DLTs as defined above and safety stopping bounds for DLTs as described in [Section 8.2.2](#). Guidelines for dose reductions of azacitidine due to toxicity or dose delays/holding for daratumumab toxicity are detailed in [Section 5.5](#).

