8.2 Analyses

Analyses Population

Analysis of primary and secondary efficacy variables will be based on the response-evaluable population, which includes all subjects who have measurable disease and received at least 2 cycles of study treatment, and have at least 2 efficacy evaluation assessments. All safety analyses for AEs will be based on the safety analysis set, which includes all subjects who receive at least 1 cycle of study treatment.

Safety Analysis

The study will begin with accrual of 6 patients in a safety run-in with interim safety analysis occurring after these 6 patients have completed at minimum Cycle 1 and further accrual stopped until safety analysis completed. If $\geq 2/6$ patients in the safety cohort have dose limiting toxicities (DLTs) as defined in [Section 5.4](#), then further study accrual will be halted until the study PI, co-investigators, and the DSMC can review the data, and determine whether the study should continue, be amended with a lower starting dose of azacitidine, or be closed to further accrual. Toxicities will be monitored throughout the study using CTCAE 5.0 criteria. Though we do not expect to observe DLTs during the study period, formal safety bounds based upon monitoring DLTs as defined in [Section 5.4](#) will guide decisions about early stopping due to potential safety concerns. A Pocock-type sequential boundary⁵⁹ will be used to monitor dose-limiting toxicities with the aim of keeping the probability of early stopping at around 90% if the true underlying toxicity rate is 25%. If the number of dose-limiting toxicities is equal to or exceeds the stopping boundaries detailed in the following table at any point in the study, then accrual to the study will be suspended until the study PI, co-investigators, and the DSMC can review the data, and determine whether the study should continue, be amended with a lower starting dose of azacitidine, or be closed to further accrual. With a toxicity rate of 25%, the expected number of enrolled patients before stopping for excessive toxicities is 6.5.

Table 8-1. Table: Safety monitoring bounds for DLTs

Number of subjects	Stopping boundary
6-9	≥ 2
10-14	≥ 3
15-18	≥ 4
19-23	≥ 5

Adverse Events

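### The DLT boundary has no row below 6 patients, so two DLTs among the first 2 to 5 patients settle the run-in criterion without suspending accrual; a small gap that is cheap to close

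*Combined protocol and SAP*

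**What the plan says.** Three places set the timing of the first DLT review. Section 5.4 says: "Study accrual will be stopped until these 6 patients have completed at minimum 5 weeks of treatment after starting azacitidine", and defines DLTs as listed toxicities "if they occur anytime within the first 5 weeks of starting azacitidine (anytime within Cycle 1"). Section 8.2 repeats the six-patient look ("The study will begin with accrual of 6 patients in a safety run-in with interim safety analysis occurring after these 6 patients have completed" at least Cycle 1) and halts further accrual for review by the PI, co-investigators and DSMC if 2 or more of the 6 "patients in the safety cohort have dose limiting toxicities (DLTs) as defined in" Section 5.4. Section 8.3 restates both.

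Table 8-1 and its copy in Section 8.3 give the continuous boundary: 2 DLTs at 6-9 subjects, 3 at 10-14, 4 at 15-18 and 5 at 19-23. There is no row for 1-5 subjects. Accrual is suspended if the DLT count "is equal to or exceeds the stopping boundaries detailed in the following table at any point in the study". The stated aim is "keeping the probability of early stopping at around 90% if the true underlying toxicity rate is 25"%, and the plan adds that at this rate "the expected number of enrolled patients before stopping for excessive toxicities is 6.5".

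Section 8.4 expects 2-3 patients per month. No text spaces out the first six enrolments.

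**The concern.** The number of patients with a DLT cannot fall. Once two of the first 2 to 5 patients have had one, the criterion of at least 2 of 6 is bound to be met, and the patients enrolled after that cannot change whether the review is triggered. The suspension clause does apply throughout the study, but only against tabulated bounds, and none is tabulated below 6. Read literally, enrolment may continue to patient 6 before the review starts.

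Section 1.3 describes this as the first study of the combination, names cytopenias and infections as the main risk, and gives the lead-in the task of limiting that risk. At stake is the exposure of up to four more patients after the lead-in's own criterion has been settled.

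**Working it through.** **The plan's own figures.** I applied Table 8-1 after every patient from 6 to 23, using an exact recursion on the DLT count with independent patients and a 25% DLT rate. This gives a stopping probability of 85.5% (plan: around 90%). Expected enrolment is 10.4 over all trials, or 8.3 among trials that cross (plan: 6.5). The plan's two figures are therefore not reproduced by the printed table. That is a separate matter, and nothing below depends on them.

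**How often two DLTs come early.** P(at least 2 in the first n) = 1 − (1−p)^n − n·p·(1−p)^(n−1).
- p = 25%, n = 5: 1 − 0.2373 − 0.3955 = 36.7%.
- p = 25%, n = 6: 1 − 0.1780 − 0.3560 = 46.6%.
- For n = 5 at p = 10%, 15% and 40%: 8.2%, 16.5% and 66.3%.

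**Effect of starting the bound of 2 at patient 2.** Any path with two DLTs by patient 5 also has at least two at patient 6, so the set of crossing trials is the same. Only the patient number at crossing changes.

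| DLT rate | Crossing probability (either start) | Mean N given crossing, from 6 / from 2 | Mean N over all trials, from 6 / from 2 |
|---|---|---|---|
| 10% | 27.7% | 8.5 / 7.9 | 19.0 / 18.8 |
| 25% | 85.5% | 8.3 / 7.3 | 10.4 / 9.6 |
| 40% | 99.2% | 6.8 / 5.1 | 7.0 / 5.3 |

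Check at 25%: the second DLT falls on patient n with probability (n−1)(0.25²)(0.75^(n−2)), which is 0.0625, 0.0938, 0.1055 and 0.1055 for n = 2 to 5. Patients saved = 4(0.0625) + 3(0.0938) + 2(0.1055) + 1(0.1055) = 0.85 per trial, matching 10.40 − 9.55. Among the 36.7% of trials concerned this is 0.85/0.367 = 2.3 patients, with a maximum of 4.

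**Allowing for accrual during the DLT window.** The table assumes that each DLT is known before the next patient enrols. At 2-3 patients per month (one every 10-15 days, taking a month as 30 days), about 35/15 = 2.3 to 35/10 = 3.5 patients arrive during one 5-week window. Much of the saving is therefore out of reach.

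I simulated exponential gaps between arrivals, with a DLT becoming known uniformly over weeks 0-5, uniformly over weeks 2-5, or only at week 5. These arrival and reporting patterns are my assumptions; the accrual rate and window are the plan's.
- 25% DLT rate: chance of sparing at least one patient 8-25%; mean spared 0.13-0.50 per trial.
- 40% DLT rate: chance 18-49%; mean spared 0.3-1.0 per trial.
- 10% DLT rate: mean spared below 0.1 per trial.

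The low end is 3 patients per month with DLTs known only at week 5. The high end is 2 per month with DLTs known uniformly over the window.

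**The case against.** The strongest reply is that nothing obliges the investigators to enrol up to patient 6. The bounds apply throughout the study, toxicities are monitored throughout, and a six-patient criterion can sensibly be acted on as soon as it is met. This is a fair reading, and it limits the point to a gap in the written rule. It does not remove the gap: the table's first row and the timing sentences in 5.4, 8.2 and 8.3 all point to a first assessment at 6.

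A reader might infer that the first five patients are unprotected. The documents do not support that. Appendix 2 provides monthly site committee review of Grade 3-5 events and DSMC review of SAEs, with meetings every six weeks. Section 7.7 requires notice of a related death within one business day, and Section 5.5 has patient-level rules. None of these is a DLT-count rule that suspends accrual, but two early DLTs would be seen.

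A reader might also infer that an earlier start is free because the crossing probability is unchanged. It is not quite free. Crossing opens a review that can continue, amend or close the study, and 2 of 2 or 2 of 3 informs that decision less than a result in 6 patients. At a 10% DLT rate the same 27.7% of trials suspend, some of them on fewer patients. This part of the objection stands, as does the point that the 36.7% and the fall from 8.3 to 7.3 overstate what is achievable at the planned accrual rate.

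**Conclusion.** The point holds as a minor gap in the written rule. Two DLTs among patients 2 to 5 settle the run-in criterion but, as written, do not suspend accrual before patient 6. At most four patients are affected. At a 25% DLT rate the realistic gain from closing the gap is 0.13-0.50 patients per trial, rising to 0.3-1.0 at 40%, with no change in the crossing probability. The cost is a review that may begin with fewer than 6 patients' data.

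The documents do not support a stronger conclusion that the boundary misses toxic regimens because it starts at 6: every trial caught by the earlier start is also caught at patient 6.

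The result assumes independent patients with a constant DLT rate, and that a patient who leaves during Cycle 1 because of a DLT still counts. The second assumption needs care, because Section 8.2 limits the safety analysis set to patients with at least one cycle and places the look after six have completed Cycle 1. The accrual-adjusted figures also rest on the arrival and reporting assumptions given in the working.

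**What to change.** For the sponsor and DSMC to adopt: change the first row from 6-9 to 2-9 in Table 8-1 and in its copy in Section 8.3. Add one sentence in each of Sections 5.4, 8.2 and 8.3 saying that accrual is suspended for PI and DSMC review as soon as the bound of 2 is met, and that the six-patient pause otherwise stays. The sentences are needed because the row change alone would sit awkwardly beside text that places the first analysis after six patients have completed Cycle 1.

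The cost is two table cells and three sentences. The sample size and the boundary's crossing probability at any DLT rate do not change. The review may sometimes start on fewer than 6 patients.

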8.1 Sample Size Determination

This is a single-arm, open-label, 2-stage phase II study designed to evaluate the efficacy of daratumumab in combination with azacitidine and dexamethasone in RRMM patients previously treated with daratumumab. A Simon's two-stage design⁵⁸ will be used for this study. The study will begin with accrual of 6 patients in a safety run-in. Safety monitoring bounds for study termination based on DLTs are described in [Section 8.2.2](#). If the safety stopping bounds are not met, study will continue to accrue more Stage I patients.

Sample size calculation was based on assessing the overall response rate (ORR) using Simon's minimax 2-stage design. Interim analysis for efficacy, using ORR, will be performed when the last patient enrolled to Stage 1 has received at least 2 cycles of treatment.

The overall target sample size of 23 patients is based upon having sufficient information to assess whether combined treatment of daratumumab with azacitidine and dexamethasone increases the ORR in this study population of RRMM patients with prior treatment with daratumumab. Data from ongoing clinical trial evaluating the safety, pharmacokinetics, and efficacy of isatuximab in patients with RRMM previously treated with daratumumab has shown preliminary results of ORR 8% (NCT02514668). Isatuximab is another CD38 monoclonal antibody with similar efficacy to daratumumab in RRMM patients.²⁴ Based on these previous results, for this study we would be interested in detecting an improvement in the ORR from a null rate of 8% to 33% ORR, which is based on the daratumumab-pomalidomide-dexamethasone

combination study in patients with RRMM re-treated with daratumumab.²³ Simon's minimax two-stage design will be used. The null hypothesis that the true response rate is 8% will be tested against a one-sided alternative that the true response rate is higher than 33%. In the first stage, 13 patients will be accrued. If there are 1 or fewer responses in these 13 patients, the study will be stopped. Otherwise, 10 additional patients will be accrued for a total of 23. The null hypothesis will be rejected if 5 or more responses are observed in 23 patients. The design will have a 90% power to reject the null hypothesis, if the true response rate is 33%, at one-sided 5% significance level. Accounting for an approximate 10% drop-out/ineligibility rate, maximum target accrual should not exceed 25 participants.

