8.3 Interim Analyses and Study Stopping Rules

As described in [Section 8.2.2](#), interim analysis will occur after accrual of 6 patients in the safety lead-in. Study accrual will be stopped until these 6 patients have completed at minimum cycle 1 of treatment, at which point a formal interim safety analysis will be performed with assessment for DLTs as defined in [Section 5.4](#) and safety stopping bounds for DLTs as described in [Section 8.2.2](#) and included again in the table below. If $\geq 2/6$ patients have DLTs, then further accrual to the study will be suspended until the study PI, co-investigators, and the DSMC can review the data, and determine whether the study should continue, be amended with a lower starting dose of azacitidine, or be closed for further accrual. Otherwise, study will continue. Safety monitoring will continue for the remaining duration of the trial. A Pocock-type sequential boundary⁵⁹ will be used to monitor dose-limiting toxicities with the aim of keeping the probability of early stopping at around 90% if the true underlying toxicity rate is 25%. The accrual will be halted until further study investigation if excessive numbers of dose-limiting toxicities are observed, that is, if the number of dose-limiting toxicities is equal to or exceeds the stopping boundaries in the following table. With a toxicity rate of 25%, the expected number of enrolled patients before stopping for excessive toxicities is 6.5.

Table: Safety monitoring bounds for DLTs

Number of subjects	Stopping boundary
6-9	≥ 2
10-14	≥ 3
15-18	≥ 4
19-23	≥ 5

As described previously in [Section 8.1](#), interim efficacy analysis will occur after completion of Simon's Stage I. 13 patients will be enrolled in Simon's Stage I. If there are 1 or fewer responses in these 13 patients, the study will be stopped. Otherwise, 10 additional patients will be accrued for a total of 23.

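### The DLT boundary printed in Table 8-1 gives neither of its two stated operating characteristics at a 25% DLT rate: it stops with probability 85.5%, not about 90%, and after about 10.4 patients on average, not 6.5

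*Combined protocol and SAP*

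**What the plan says.** Section 8.2 (Safety Analysis), repeated in Section 8.3, describes a Pocock-type boundary for DLTs chosen "with the aim of keeping the probability of early stopping at around 90% if the true underlying toxicity rate is 25" percent. Both sections add that, at the same rate, 6.5 patients are expected to be enrolled before the rule stops the trial.

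Table 8-1 is headed "Number of subjects Stopping boundary". Its limits are at least 2 DLTs at 6-9 subjects, at least 3 at 10-14, at least 4 at 15-18 and at least 5 at 19-23. In 8.2 the rule acts when the DLT count "is equal to or exceeds the stopping boundaries detailed in the following table at any point in the study"; 8.3 words it as "if the number of dose-limiting toxicities is equal to or exceeds the stopping boundaries in the following table". Crossing suspends accrual pending review by the investigators and the DSMC.

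The first formal look is at six patients, with "interim safety analysis occurring after these 6 patients have completed at minimum Cycle 1 and further accrual stopped until safety analysis completed". Section 5.4 counts toxicities as DLTs "if they occur anytime within the first 5 weeks of starting azacitidine (anytime within Cycle 1"). On size, Section 8.1 says "Otherwise, 10 additional patients will be accrued for a total of 23", and then that "maximum target accrual should not exceed 25 participants".

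**The concern.** The two figures are the only description of how well the safety rule works, and the investigators, the DSMC and the IRB will rely on them. Section 1.3 presents this as the first study of the combination, names toxicity as the main risk, and points to the stopping rules as mitigation. If the figures do not follow from the printed limits, either the protection is overstated or the printed table is not the boundary that was evaluated.

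A related gap is that the table's subject count is not defined. A DLT may take up to five weeks to appear, so patients enrolled and patients with known DLT status differ whenever accrual continues during the window.

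**Working it through.** **Inputs.** DLT rate p = 0.25, the four limits and the first look at 6 come from Section 8.2; the total of 23 comes from Section 8.1. DLT status is taken as known for every patient counted.

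**Method.** Let f_n(x) be the probability of still accruing after n patients with x DLTs. Then f_n(x) = 0.75·f_(n-1)(x) + 0.25·f_(n-1)(x-1). At each n, the probability at or above the limit is moved to stopped.

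**Stopping probability (stated: around 90%).**

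- At n = 6: 1 − 0.75^6 − 6(0.25)(0.75^5) = 1 − 0.1780 − 0.3560 = 0.4661.
- At n = 7: 0.25 × 0.3560 = 0.0890. At n = 8: 0.25 × 0.3115 = 0.0779. At n = 9: 0.25 × 0.2670 = 0.0667. The cumulative total is 0.6997.
- At n = 10 the limit rises to 3, and trials still running had at most one DLT, so none can cross. The same happens at 15 and 19.

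| Subjects | Limit | Added | Cumulative |
|---|---|---|---|
| 6-9 | 2 | 0.6997 | 0.6997 |
| 10-14 | 3 | 0.0905 | 0.7901 |
| 15-18 | 4 | 0.0328 | 0.8229 |
| 19-23 | 5 | 0.0317 | 0.8547 |

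The printed rule therefore stops with probability 85.5% and misses a 25% DLT rate with probability 14.5%, where 10% is implied. Solving for 90% gives a DLT rate of about 27.4%.

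**Other readings of the printed table.** Applying the limit of 2 from patient 1 leaves 85.5% unchanged, because two early DLTs still cross at 6. Looks at 6, 13 and 23 only give 81.1%; looks at the start of each row only give 69.8%. If the last limit is carried to 25 patients, which the table does not print, the result is 87.9%.

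**Expected number (stated: 6.5).** With a first look at 6, E[N] = 6 + Σ(n = 6 to 22) P(not stopped by n). The first term alone is 1 − 0.4661 = 0.534, so E[N] already exceeds 6.5. In full, the sum of n × P(stop at n) is 7.056:

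- Overall: 7.056 + 23 × 0.1453 = 10.4.
- Among trials that stop: 7.056 / 0.8547 = 8.3.
- Monitored from patient 1: 9.6 overall and 7.3 given stopping.

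**Where the stated figures may come from.** Adding an unprinted limit of at least 1 DLT at patients 3-5 to the printed rows gives 90.6% and 6.5 patients overall. The match is not unique in kind: a limit of 1 at patients 1-4 gives 89.6% and 6.3, and at patients 1-5 gives 90.6% and 5.8 (any patients left below 6 having a limit of 2).

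**If the count means enrolled patients.** Section 8.4 expects 2-3 patients per month. Five weeks is 35/30.44 = 1.15 months, so about 2.3 to 3.5 patients are in the window at any time. As an illustration, 7 patients with completed windows and 2 DLTs meet the limit of 2; with 3 more enrolled the count is 10, where the limit is 3. Simulation (40,000 trials per setting, evenly spaced accrual, pause at 6, follow-up completed after the last patient) gives:

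| Patients/month | DLT known at week 5 | Onset uniform over 5 weeks |
|---|---|---|
| 2 | 81.4% | 84.2% |
| 2.5 | 81.2% | 83.8% |
| 3 | 79.7% | 83.2% |

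At the slower accrual implied by the 12-18 months in Section 3.1 (23/18 = 1.3 to 23/12 = 1.9 per month), the range is about 81.8% to 84.7%.

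**The case against.** The plan words 90% as an aim and as approximate; the shortfall is 4.5 points; and crossing leads to a review, not automatic closure. Grade 3-5 events are also reviewed monthly and serious events by the DSMC (Appendix 2). All of that stands and limits the consequence: no efficacy conclusion depends on this figure. It does not remove the mismatch, because 6.5 carries no such qualifier and cannot be the overall average under a first look at 6.

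The subject count also has a natural reading. The first look requires completed Cycle 1, and the safety set in 8.2 requires at least one cycle, which is the DLT window. Against this, Section 7.2 defines safety analyses by one dose, and the 6.5 refers to enrolled patients. A one-line definition is warranted, no more.

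A reader might infer three stronger things.

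- That the real stopping probability is some single figure such as 81-82%. The documents do not support this: it needs the enrolled reading plus assumptions about accrual and DLT timing that they do not fix.
- That early rows were dropped from the table, or that the table is wrong. The match with an unprinted early limit is suggestive, but nothing in the documents says which boundary was meant.
- That patients 24 and 25 are unprotected. The 25 is an allowance for drop-out and ineligibility, so there is a gap only if more than 23 patients become DLT-evaluable.

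**Conclusion.** The concern holds as a mismatch between a printed rule and its stated properties. For Table 8-1 as printed, with DLT status known for every counted patient and a look after each one, the stopping probability at a 25% DLT rate is 85.5%, and the expected number of patients is about 10.4 (8.3 given stopping). These results are exact and assume independent patients with a common DLT rate. The enrolled-count range of roughly 80-84% is conditional on 2-3 patients per month and on when DLTs become known; it shows why the count needs a definition and is not a second headline result. That the stated figures belong to another boundary is an inference. The calculation does not show which boundary is right.

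**What to change.** In Sections 8.2 and 8.3, reconcile Table 8-1 with the two stated figures.

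- If the printed table is the rule, state a stopping probability of about 85% and an expected number of about 10.4 patients (8.3 among trials that stop), with the first look at 6. If another boundary was intended, print it in full with its own figures.
- State that the table's subject count is patients who have completed the five-week DLT window or had a DLT.
- State whether the boundary applies to any DLT-evaluable patients beyond 23 and, if so, recompute both figures. For illustration only, carrying the last limit to 25 would give 87.9%, so the 85% would no longer apply.

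If the printed table stands, the cost is wording only: no extra patients or data are needed, and the stated protection becomes slightly less favourable.

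### Sections 8.2 and 8.3 count patients for the lead-in safety rule but, read literally, count toxicities for the Table 8-1 boundary, so one patient with two DLTs can give opposite accrual decisions

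*Combined protocol and SAP*

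**What the plan says.** Section 8.2 (Safety Analysis) sets two triggers in one paragraph.

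- **Lead-in rule.** Accrual is halted if at least 2 of the 6 "patients in the safety cohort have dose limiting toxicities (DLTs) as defined in" Section 5.4. The unit is the patient. Section 8.3 repeats the rule and adds what follows if it is not met: "Otherwise, study will continue".
- **Continuous boundary.** Accrual is suspended under this condition: "If the number of dose-limiting toxicities is equal to or exceeds the stopping boundaries". Section 8.3 has the same wording: "excessive numbers of dose-limiting toxicities are observed, that is, if the number of dose-limiting toxicities is equal to or exceeds the stopping boundaries". The unit, as written, is the toxicity.

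The boundary table ("Safety monitoring bounds for DLTs") requires at least 2 at 6-9 subjects, 3 at 10-14, 4 at 15-18 and 5 at 19-23. Its columns give the number of subjects and the stopping boundary, but not what the boundary counts. The stated aim is a stopping probability of around 90% at a true toxicity rate of 25%, with 6.5 patients expected before stopping.

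Section 5.4 defines the events: "Dose-limiting toxicities are defined as the following toxicities if they occur anytime within the first 5 weeks of starting azacitidine". Grade 4 neutropenia beyond 7 days and Grade 4 thrombocytopenia beyond 7 days despite transfusion are separate items. No section says that a patient contributes at most one DLT.

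**The concern.** The two triggers overlap at the first formal safety look, where both have a threshold of 2 but different units. Suppose one of the six lead-in patients has both prolonged cytopenias in Cycle 1, attributed to the combination, and the other five have no DLT. The lead-in rule sees 1 of 6 and the study continues. The literal Table 8-1 rule sees 2 toxicities and accrual is suspended. A study team and a monitoring committee could each follow a sentence of the protocol and disagree, after the data are known, on whether a prespecified trigger was met. The boundary's operating characteristics also have no definite meaning until the unit is fixed.

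**Working it through.** **Inputs from the documents.** Table 8-1 bounds; 23 patients; a 25% toxicity rate (Sections 8.2 and 8.3).

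**Assumptions, not in the documents.** A true per-patient DLT rate *p* of 10%, used beside the protocol's 25%. An overlap *s*, the share of DLT patients who have two DLTs, of 0, 5, 10, 20 or 50%. Patients are independent, and the boundary is checked after every patient from the 6th to the 23rd.

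**Step 1: the plan's own figures, counting patients.** At *p* = 0.25 the chance of meeting the bound at six patients is 1 − 0.75⁶ − 6 × 0.25 × 0.75⁵ = 1 − 0.1780 − 0.3560 = 0.466. An exact recursion to patient 23 gives a stopping probability of 85.5%, against around 90% stated. Expected enrolment is 10.4, or 8.3 among trials that stop, against 6.5 stated. With looks from patient 6, 46.6% stop at 6 and the rest at 7 or later, so the mean cannot be below 6 × 0.466 + 7 × 0.534 = 6.53. The stated figures therefore do not reproduce on this unit.

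**Step 2: the first look, counting toxicities.** A DLT patient now contributes 2 with probability *s* and 1 otherwise. The bound is missed only if there are no DLT patients, or exactly one with a single DLT:

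P(suspend at 6) = 1 − (1 − *p*)⁶ − 6*p*(1 − *s*)(1 − *p*)⁵

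At *p* = 0.10 this is 1 − 0.5314 − 0.3543 × (1 − *s*) = 0.1143 + 0.3543 × *s*. It gives 11.4% at *s* = 0 (the patient count), 18.5% at *s* = 20% and 29.1% at *s* = 50%.

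**Step 3: probability of ever suspending by patient 23 (exact recursion).**

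| Assumed overlap *s* | *p* = 10% | *p* = 25% |
|---|---|---|
| 0 (same as counting patients) | 27.7% | 85.5% |
| 5% | 30.9% | 86.9% |
| 10% | 34.0% | 88.3% |
| 20% | 39.9% | 90.6% |
| 50% | 54.7% | 95.2% |

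The two counts agree when no patient has two DLTs and move apart as the overlap grows.

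**The case against.** The strongest reply is that the context already settles the unit. Section 8.3 says the six-patient look uses the table's bounds and then states that look as at least 2 of 6 patients, which is the table's first row in patients. The bounds are indexed by number of subjects, and the 25% toxicity rate is naturally a per-patient quantity. This stands as evidence of intent. A reader might infer from the literal wording that the design is event-based; the documents do not support that. None of these signs is stated as the counting rule, though, and the operative sentence says something else in two sections.

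Second, the consequence is mild. Meeting the bound suspends accrual until the investigators and the DSMC have reviewed the data, and continuing is a listed outcome. They would see that both DLTs came from one patient. This also stands: one patient cannot close the study under either reading.

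Third, a reader might take the azacitidine safety table (Table 1-2) as proof that the overlap is large. With 107 of 175 patients having Grade 3/4 neutropenia and 102 of 175 thrombocytopenia, at least 107 + 102 − 175 = 34 (19%) had both. That is a different event. Those were MDS patients with a mean exposure of 12.2 months, Grade 3 was included, and any duration counted. The best-supportive-care arm had 22% and 28%. A DLT here must be Grade 4, last more than 7 days, fall within five weeks and be attributed to the combination. Entry requires an ANC of at least 1,500/mcL and platelets of at least 75,000/mcL, and G-CSF is allowed in Cycle 1 once neutropenia reaches Grade 3. The table therefore does not support an overlap of 20-50%, nor a claim that false suspensions would be far more frequent.

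Finally, toxicity counting comes near 90% at *p* = 25% when the overlap is about 20%. It would be wrong to conclude that the plan's figure was derived that way: no overlap is documented, and expected enrolment in that case is 9.5, not 6.5.

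**Conclusion.** The inconsistency holds as a defect of wording in a prespecified decision rule. Followed literally, the two rules give opposite accrual decisions at the first look for a patient pattern that Section 5.4 makes possible. A per-patient count is very likely what was meant. The numerical effect is illustrative only: it runs from nil at zero overlap to about 27 percentage points at a 10% DLT rate (27.7% to 54.7%) and about 10 points at 25% (85.5% to 95.2%) at the extreme overlap of 50%. It rests on an assumed overlap, an assumed 10% rate and a check after every patient. At small overlaps the difference is a few points. The correction is worth making because it costs almost nothing and removes a possible dispute over an accrual hold.

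**What to change.** Reconcile the passages to the per-patient unit that the 2/6 rule and the boundary design already use. In Sections 8.2 and 8.3, word the boundary as *the number of patients with at least one dose-limiting toxicity*, and label the boundary column of the table in both sections *Patients with ≥1 DLT*. The bounds, the DLT definition, the sample size and data collection do not change.

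The cost is two sentences and a column label. The downside is that two DLTs in one patient would no longer trigger a formal suspension by themselves. Under Appendix 2, Grade 3-5 adverse events are still reviewed monthly by the Site Committee and serious ones by the DSMC. A prolonged Grade 4 cytopenia that is not classed as serious is not shown to reach the DSMC by that route.

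Fixing the unit also exposes a separate item: at a 25% rate the per-patient boundary stops with probability 85.5%, with 10.4 patients expected. The stated figures of around 90% and 6.5 need their own correction.
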